### **7.3.2 Secondary endpoint analyses**

For the key secondary endpoint, proportion of patients with disease progression as defined by FVC decline  $\geq 10\%$  or death over week 52, two main analyses are planned.

Firstly, in order to assess the predictive value of change in extracellular matrix (ECM) biomarker CRPM over 12 weeks for disease progression as defined by FVC decline  $\geq 10\%$  or

death over 52 weeks, a logistic regression (or a similar appropriate) analysis including baseline blood CRPM and the rate of change (slope) in blood CRPM over the first 12 weeks as covariates will be applied for the placebo treated patients only.

Secondly, in order to assess how nintedanib treatment during the first 12 weeks affects the association between change in extracellular matrix (ECM) biomarker CRPM over 12 weeks and disease progression, a logistic regression (or a similar appropriate) analysis including baseline blood CRPM, rate of change (slope) in blood CRPM over the first 12 weeks, treatment and treatment CRPM slope interaction as covariates will be applied. The interaction term will be of primary interest within this analysis. More details will be given in the TSAP. Both analyses will be repeated for rate of change (slope) in the biomarkers C1M and C3M defined as secondary endpoints. Reasonably, baseline CRPM as covariate will be replaced by baseline C1M/C3M in these analyses.

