With the introduction of nintedanib in the treatment algorithm of IPF, there is an additional need to further characterize its profile in patients at an early disease stage, i.e. in patients with limited lung volume impairment, and to address the question when to start treatment in these patients. Currently, many physicians apply a wait and watch strategy for these patients as there are no markers to predict the individual course in a given patient or response to treatment which may result in a delay of treatment initiation. Identifying biomarkers to predict the clinical course and benefits of therapy for a given patient early in the course of the disease remains one of the most urgent and relevant challenges in patient management

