## 2.3 BENEFIT - RISK ASSESSMENT

The favourable benefit-risk ratio based on the so far acquired knowledge about nintedanib is the rationale to conduct further studies with nintedanib in idiopathic pulmonary fibrosis.

As described in [Section 1](#), patients with IPF, including patients with only limited FVC impairment, may benefit from lesser decline in lung function and hence slower disease progression as a result of treatment with nintedanib [\[P15-09946\]](#). In addition, nintedanib significantly reduced the risk of first acute exacerbation in 2 out of 3 clinical trials [\[P11-11216, P14-07514\]](#).

Two thirds of the patients in this trial will be treated with placebo for the first 12 weeks of the trial. A 1:2 randomization (nintedanib:placebo) increases the number of patients treated with placebo during the first 12 weeks and consequently increases the power of assessing the association between change in the extracellular matrix (ECM) biomarker CRPM over 12 weeks and disease progression in placebo treated patients. Change in the extracellular matrix (ECM) biomarker CRPM over 12 weeks will be classified as stable or falling [ $\leq 0$  ng/ml/month] or rising [ $> 0$  ng/ml/month] in line with the PROFILE cohort [R15-1220]. A 12 week placebo period is considered acceptable given that the in- and exclusion criteria assure inclusion of patients with mostly preserved lung function at baseline. In addition, it is unclear if patients would even receive antifibrotic treatment as in clinical practice. IPF patients with limited lung function impairment might not be reimbursed in some countries depending on a FVC % predicted threshold (e.g.  $>80\%$  predicted).

Following the 12 week placebo controlled period all patients in this trial will continue further treatment with nintedanib. This will allow active treatment also to patients previously on placebo. In the subgroup of patients by baseline FVC ( $>80\%$  versus  $\leq 80\%$  predicted) in the pooled INPULSIS data set, the risk of disease progression (time to FVC decline  $>10\%$  or death) up to 12 weeks was low and similar in patients treated with placebo and nintedanib (approximately 10% of patients, respectively), although there was a risk reduction in favour of nintedanib by approx. 40% in the end of the 52 week treatment period for both subgroups and a consistent effect on reducing the annual rate of decline by 50%, similar to the primary outcome in the overall population [P15-09946].

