#### **5.1.2 Secondary Endpoints**

The key secondary endpoint is the proportion of patients with disease progression as defined by absolute FVC (% predicted) decline  $\geq 10\%$  or death until week 52 based on in clinic supervised spirometry.

Secondary endpoints are the rate of change (slope) in blood C1M from baseline to week 12 and the rate of change (slope) in blood C3M from baseline to week 12.

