Table 2 gives the calculated sample size numbers for assumed relative treatment differences of 20 and 30 percent.

Table 7.7:2 Sample sizes for common standard deviations of 30%, 40%, and 50%; significance level 5%; power 90% with a 1:2 randomisation ratio nintedanib:placebo

Sample sizes for common standard deviations of 30%, 40%, and 50%; significance level 5%; power 90% with a 1:2 randomisation ratio nintedanib:placebo									
	Common STD 30%			Common STD 40%			Common STD 50%		
	n			n			n		
	nintedanib	placebo	total	nintedanib	placebo	total	nintedanib	placebo	total
20%	37	73	110	64	128	192	100	199	299
30%	17	33	50	29	58	87	45	89	134

If the true standard deviation of change in CRPM relative to baseline lies between 30 and 50 percent, a total number of patients between 110 and 300 would be needed to detect a

treatment group difference of 20% with a power of 90% with a treatment allocation ratio of 1:2 (Nintedanib:Placebo).

However, the key secondary endpoint requires more patients for two reasons: firstly, only patients initially treated with Placebo are analysed in the first step (reducing the actual sample size for this analysis to 2/3 of the total sample size) and secondly, some loss of information is associated with the planned analysis due to the binary state of the endpoint. To be more precise, with n=350 randomised patients, n=233 patients will be initially treated with Placebo and based on the INPULSIS results [[P14-07514](#)], we expect to observe a total of about 40% of disease progression as defined by FVC decline  $\geq 10\%$  or death over week 52 for that treatment group. Using available data from the observational PROFILE study [[R15-1220](#)], we further expect roughly half of the patients to have rising biomarker values (slope greater than zero) and the remaining patients having stable biomarker values (slope less or equal to zero) resulting in about equally sized groups if the rate of change (slope) in blood CRPM from baseline to week 12 is dichotomized. With the stated sample size, an absolute difference in rates of at least 20% (i.e. 30% vs 50% of patients with disease progression) can be detected with a power of 88%.

For these reasons, a sample size of n=350 patients (117 on nintedanib and 233 on placebo) is planned for this study.

Calculations were performed using nQuery Advisor® 6.1.1 statistical package by Statistical Solutions Ltd.

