7.5 SECONDARY ENDPOINT(S)

7.5.1 Key secondary endpoint(s)

The key secondary endpoint is defined as the proportion of patients with disease progression as defined by absolute FVC (% predicted) decline $\geq 10\%$ or death until week 52.

The following analyses are planned:

- Firstly, in order to assess the association of change in extracellular matrix (ECM) biomarker CRPM over 12 weeks with disease progression as defined by FVC decline $\geq 10\%$ or death over 52 weeks, a logistic regression analysis including baseline blood

CRPM and the rate of change (slope) in blood CRPM over the first 12 weeks as covariates will be applied **for the placebo treated patients only**.

By doing this, the potential of CRPM as a prognostic biomarker is evaluated.

- Secondly, in order to assess how Nintedanib treatment during the first 12 weeks affects the association between change in extracellular matrix (ECM) biomarker CRPM over 12 weeks and disease progression, a logistic regression analysis including baseline blood CRPM, rate of change (slope) in blood CRPM over the first 12 weeks, treatment and treatment CRPM slope interaction as covariates will be applied. **The interaction term will be of primary interest within this analysis.**
- Thirdly, in order to assess whether the overall treatment regimen affects disease progression as defined by FVC decline $\geq 10\%$ or death over 52 weeks, a logistic regression analysis including baseline blood CRPM and randomized treatment as covariates will be applied. **The treatment effect will be of primary interest within this analysis.**
- Fourthly, in order to assess whether rate of change (slope) in blood CRPM over the first 12 weeks to some extent explains the effect of treatment regimen on disease progression as defined by FVC decline $\geq 10\%$ or death over 52 weeks, a logistic regression analysis including baseline blood CRPM, rate of change (slope) in blood CRPM over the first 12 weeks and randomized treatment as covariates will be applied. **The treatment effect will be of primary interest within this analysis.**

Patients who died or progressed in the blinded phase are not at risk in the open label period, but will be considered in the main analysis (including their progression and/or death).

The four main analyses of the key secondary endpoint outlined at the beginning of this section will be repeated by replacing CRPM by C1M and C3M, respectively.

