7.5.2 Other Secondary endpoints

The following secondary endpoints are defined:

- Rate of change (slope) in blood C1M from baseline to week 12
- Rate of change (slope) in blood C3M from baseline to week 12

Please refer to Section 7.3.2 of the CTP for further details of the analysis.

This endpoint will be analyzed in a similar manner as the primary endpoint. Reasonably, baseline CRPM as covariate will be replaced by baseline C1M and C3M in these analyses.

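### The visible progression models omit baseline FVC % predicted, so they cannot show what CRPM slope adds to lung function at entry, and the fourth SAP model could credit slope with part of a treatment effect it does not carry

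*Protocol*

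**What the plan says.** Protocol 5.1.2 defines the outcome: "The key secondary endpoint is the proportion of patients with disease progression as defined by absolute FVC (% predicted) decline" of at least 10%, or death, until week 52.

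The progression models that can be seen are these:

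| Model | Where | Covariates |
|---|---|---|
| First, placebo patients only | Protocol 7.3.2, SAP 7.5.1 | baseline CRPM, CRPM slope |
| Second | Protocol 7.3.2, SAP 7.5.1 | baseline CRPM, CRPM slope, treatment, treatment-by-slope interaction |
| Third | SAP 7.5.1 | baseline CRPM, randomised treatment |
| Fourth | SAP 7.5.1 | baseline CRPM, CRPM slope, randomised treatment |

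The first model pairs baseline CRPM with "the rate of change (slope) in blood CRPM over the first 12 weeks as covariates will be applied for the placebo treated patients only". The fourth asks whether "rate of change (slope) in blood CRPM over the first 12 weeks to some extent explains the effect of treatment regimen on disease progression", with a regression "including baseline blood CRPM, rate of change (slope) in blood CRPM over the first 12 weeks and randomized treatment as covariates will be applied". The C1M and C3M repeats change only the biomarker.

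Protocol 7.7 names the first model as a reason for going to 350 patients, since "only patients initially treated with Placebo are analysed in the first step". Protocol 1.1 gives the clinical motive: "Currently, many physicians apply a wait and watch strategy for these patients as there are no markers to predict the individual course".

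**The concern.** The models adjust for the marker's starting value but not for the starting value of the outcome. Two consequences follow, of different kinds.

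For the first model, the slope coefficient includes anything slope shares with lung function at entry. That is acceptable for confirming an association. It leaves open the question a treating physician would ask, because that physician already knows the patient's FVC and wants to know what three months of CRPM measurements add. Protocol 2.3 itself notes that antifibrotic treatment "might not be reimbursed in some countries depending on a FVC % predicted threshold".

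For the fourth model the issue is interpretation. Slope is measured after randomisation, so randomisation does not protect its relation with progression. If baseline lung function is related to both slope and progression, a slope with no effect of its own will pick up part of the lung-function effect. If nintedanib also moves slope, the treatment coefficient shifts between the third and fourth models, and the shift can be read as mediation.

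**Working it through.** **The plan's own figure.** Protocol 7.7 gives 88% power for 30% against 50% progression in two equal halves of 233 placebo patients. With n = 116.5 per half, pooled rate 0.40 and two-sided alpha 0.05:

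Power = Φ[(0.20 − 1.96·√(2·0.40·0.60/116.5)) / √((0.30·0.70 + 0.50·0.50)/116.5)] = 0.881.

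The 88% reproduces. No stated figure is wrong; the point is what the models contain.

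**Assumed inputs.** The documents give neither the correlation r between CRPM slope and baseline lung function (worse lung function, steeper slope) nor the odds ratio (OR) for progression per SD of worse lung function. Both are varied below.

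**First model.** Logistic simulation with N = 233, 40% progression, baseline CRPM in every model (OR 1.2 per SD, uncorrelated with slope), and slope with no effect beyond lung function. Share of trials in which slope is significant:

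| r | OR per SD | Without FVC | With FVC |
|---|---|---|---|
| 0.2 | 1.5 | 8.8% | 5.0% |
| 0.2 | 2.0 | 15.4% | 5.4% |
| 0.3 | 1.5 | 13.2% | 4.9% |
| 0.3 | 2.0 | 28.8% | 5.0% |

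At OR 1.25 (r = 0.2 to 0.3) the share without FVC is 6% to 8%; at r = 0.1 it is 5% to 8%; at r = 0 it is about 5%, so there is no excess. With baseline CRPM and slope correlated at −0.3 and FVC truncated at 80% predicted (underlying mean 90, SD 15, assumed), the four rows without FVC become 8% to 25%.

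The crude slope OR in the tabulated settings is 1.08 to 1.22 per SD, or about 3 to 7 points between the rising and stable halves. The 20-point design difference needs about 1.73 per SD.

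**Third against fourth model.** To a first approximation:

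share explained ≈ ln(crude slope OR) × slope shift under nintedanib (in SD) / |ln(treatment OR)|.

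With an assumed treatment OR of 0.65 (|ln| = 0.431) and an assumed shift of 0.3 to 0.5 SD:

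- low end (r = 0.2, OR 1.5): ln(1.08) × 0.3 / 0.431 = 0.077 × 0.3 / 0.431 = 5.4%
- high end (r = 0.3, OR 2.0): ln(1.215) × 0.5 / 0.431 = 0.195 × 0.5 / 0.431 = 22.6%

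Large-sample simulation gives 5.5% and 23.3% at the same corners, about 0% once lung function is in both models, and about 0% at r = 0 either way. A negative r would hide an effect instead.

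**Noise at the actual size.** With N = 350, treatment OR 0.65 and r = 0, the 5th to 95th percentile range of the share explained is about −27% to +23% (shift 0.3 SD) or −44% to +41% (shift 0.5 SD). Treatment is significant in only about 40% of such trials.

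**Cost in information.** Expected placebo events are 0.40 × 233 = 93.2. Two covariates leave 93.2/2 = 47 events per term; three leave 93.2/3 = 31. At r = 0, adding FVC raises power by 0 to 4 points (for example 71.7% to 75.6% at slope OR 1.5 and lung-function OR 2.0).

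**Is adjustment neutral?** Not entirely. Measured baseline FVC is part of the change outcome. When slope relates to true FVC level but not to decline (assumed r = 0.2 to 0.3, measurement SD 3 to 5 points), the adjusted first model rejects in about 5% to 11% of trials, against about 4.5% to 6.5% unadjusted. The cause is regression to the mean.

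**The case against.** **The plan did not ask this question.** Protocol 2.2 sets out to confirm an association seen in an earlier cohort, mainly in placebo patients, and protocol 7.7 powers an unadjusted contrast. Neither document promises information beyond FVC, and the reimbursement remark in protocol 2.3 defends the placebo period; it does not describe how a marker will be used. This stands. A reader might infer that the first model is invalid, or that the 9% to 29% in the table are false positives. The documents do not support that: those are real crude associations, and the crude association is the stated aim.

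**The adjustment may already exist.** The SAP abbreviation list defines BFVC as baseline FVC although no visible text uses it, Section 9.1 with the SAS code is not available, and Table 6.1: 1 names a sensitivity analysis for this endpoint (visible only as starting at Visit 5). So it cannot be concluded that the plan lacks an adjusted model, only that the visible models do.

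**The size is assumed.** This also stands. Entry at FVC of at least 80% predicted narrows baseline FVC, which makes an OR of 2.0 per SD a strong assumption. The treatment OR of 0.65 is unsupported too: both arms take nintedanib from week 12, and protocol 2.3 reports similar 12-week progression risk on drug and placebo. Much of the fourth-model bias lies within the noise shown above. Noise does not remove a systematic shift, but it limits what anyone should conclude from that model, with or without FVC.

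**Conclusion.** The point holds as a limit on interpretation, with an inexpensive improvement available; it is not an error or an internal contradiction. No visible progression model contains baseline FVC % predicted. The first model answers its own question but not whether slope adds to entry lung function. The case is clearest for the fourth model, where an inert slope could appear to explain about 5% to 23% of the treatment effect under the assumed r of 0.2 to 0.3, OR of 1.5 to 2.0, treatment OR of 0.65 and slope shift of 0.3 to 0.5 SD. The bias is nil at r = 0, and its true size cannot be found from the documents.

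Three stronger inferences are not supported. The third model's total treatment effect is not confounded by the omission, because randomisation protects it. Lung function alone would not produce the 20-point design difference under any tabulated setting. And adding FVC would not turn the fourth model into proof of mediation: other shared causes remain, and the odds ratio is non-collapsible, so the treatment coefficient can change between the third and fourth models for that reason alone.

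**What to change.** If withheld SAP text already adjusts for baseline FVC, point to it. Otherwise:

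- Add baseline FVC % predicted, continuous and by the SAP 6.7 baseline rule, to the third and fourth models, with covariates otherwise identical apart from slope. The comparison between the two carries the claim about explanation.
- Report an FVC-adjusted version of the first and second models beside the planned versions, and do the same for the C1M and C3M repeats. Keep the planned first model, which answers the stated aim.
- Label the fourth analysis exploratory and say why.

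The cost is SAP wording and one model term. Supervised spirometry is already done at Visits 1 and 2, and 31 events per term in the placebo-only model is ample. State two downsides: the adjusted odds ratio is a different quantity from the unadjusted one, and adjusting for a measured baseline that enters the change outcome can introduce a small regression-to-the-mean bias. Neither version alone should be treated as definitive.

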#### **7.3.4 Safety analyses**

Adverse events will be coded using the Medical Dictionary for Regulatory Activities (MedDRA) coding dictionary. Standard BI summary tables and listings will be produced. All adverse events with an onset between start of treatment and end of the residual effect period (REP), a period of 28 days after the last dose of trial medication, will be assigned to the treatment period for evaluation. All treated patients will be included in the safety analysis. In general, safety analyses will be descriptive in nature and will be based on BI standards. No hypothesis testing is planned.

Statistical analysis and reporting of adverse events will concentrate on treatment-emergent adverse events. To this end, all adverse events occurring between start of treatment and end of the residual effect period will be considered 'treatment-emergent'. The residual effect period is defined as 28 days. Adverse events that start before first drug intake and deteriorate under treatment will also be considered as 'treatment-emergent'.

Frequency, severity, and causal relationship of adverse events will be tabulated by system organ class and preferred term after coding according to the current version of the Medical Dictionary for Drug Regulatory Activities (MedDRA).

Laboratory data will be analysed both quantitatively as well as qualitatively. The latter will be done via comparison of laboratory data to their reference ranges. Values outside the reference range as well as values defined as clinically relevant will be highlighted in the listings. Treatment groups will be compared descriptively with regard to distribution parameters as well as with regard to frequency and percentage of patients with abnormal values or clinically relevant abnormal values.

Vital signs, physical examinations, or other safety-relevant data observed at screening, baseline, during the course of the trial and at the end-of-trial evaluation will be assessed with regard to possible changes compared to findings before start of treatment.

## **7.4 INTERIM ANALYSES**

No interim analysis is planned.

## **7.5 HANDLING OF MISSING DATA**

### **7.5.1 Efficacy endpoints**

In efficacy analyses of continuous endpoints, missing data will not be imputed. In the analyses of the time-to-event endpoints, missing or incomplete data are managed by standard survival analysis techniques. These will be described in detail in the TSAP.

In the analyses of the categorical endpoints, missing data will be imputed using the worst case.

### 7.5.2 Safety endpoints

Missing or incomplete AE dates will be imputed according to BI standards. With respect to other safety evaluations, it is not planned to impute missing values.

## 7.6 RANDOMISATION

Patients will be randomised in blocks to double-blind treatment with an unequal probability 1 to 2 of assignment to nintedanib and placebo. BI will arrange for the randomisation and the packaging and labelling of trial medication. The randomisation list will be generated using a validated system, which involves a pseudo-random number generator so that the resulting treatment will be both reproducible and non-predictable. The block size will be documented in the CTR. Access to the codes will be controlled and documented. All members of the Medical Project Team will remain blinded to the randomisation schedule until after the final database is locked.

## 7.7 DETERMINATION OF SAMPLE SIZE

The sample size calculations are based on change relative to baseline in biomarker levels of serum CRPM, serum C1M and serum C3M (unpublished data, no reference available). The sample size calculations are based on two-sided tests ( $\alpha = 0.05$ ) to detect a difference in means of two independent samples with a 1:2 randomisation ratio nintedanib:placebo in the samples with a power of 90%. No multiplicity adjustments are made as part of the power calculation, and no adjustment is made for a potential subject withdrawal. Sample size calculations are performed for assumed differences between treatment group and placebo of 20% and 30% difference. Due to the lack of data from respective IPF patients and since there is no evidence biomarker courses are principally different across both indications, data from two studies of RA patients are used to estimate the standard deviation over time in biomarker values relative to baseline: Study A) RA patients including a placebo group and a treatment group with measurements of serum CRPM, serum C1M and serum C3M at baseline, weeks 4, 16, and 24; and Study B) RA patients including a placebo group and a treatment group with measurements of serum CRPM, serum C1M and serum C3M at baseline, weeks 4, and 12.

The hypothesis to be tested can be formulated as:

$H_0: \mu_{\text{Treatment}} = \mu_{\text{Placebo}}$   
tested confirmatively against the alternative

$H_a: \mu_{\text{Treatment}} \neq \mu_{\text{Placebo}}$   
where  $\mu_{\text{Treatment}}$  is the change in biomarker relative to baseline in the treatment group, and  $\mu_{\text{Placebo}}$  is the change relative to baseline in the placebo group.

Table 7.7:1 Data of standard deviation over time in changes relative to baseline

Data of standard deviation over time in changes relative to baseline						
	CRPM		C1M		C3M	
	Placebo	Treatment	Placebo	Treatment	Placebo	Treatment
Study A						
Week 4	42% (n=100)	34% (n=143)	44% (n=116)	41% (n=176)	38% (n=116)	31% (n=176)
Week 16	33% (n=88)	36% (n=128)	42% (n=102)	58% (n=156)	32% (n=102)	27% (n=156)
Week 24	31% (n=83)	32% (n=131)	53% (n=97)	53% (n=162)	33% (n=97)	31% (n=162)
Study B						
Week 4	40% (n=71)	25% (n=66)	48% (n=76)	68% (n=75)	43% (n=71)	66% (n=67)
Week 12	43% (n=52)	47% (n=68)	45% (n=54)	55% (n=73)	44% (n=50)	44% (n=68)

Based on Table 7.7:1, sample sizes will be calculated for a range of common standard deviations of 30%; 40% and 50%.

Table 2 gives the calculated sample size numbers for assumed relative treatment differences of 20 and 30 percent.

Table 7.7:2 Sample sizes for common standard deviations of 30%, 40%, and 50%; significance level 5%; power 90% with a 1:2 randomisation ratio nintedanib:placebo

Sample sizes for common standard deviations of 30%, 40%, and 50%; significance level 5%; power 90% with a 1:2 randomisation ratio nintedanib:placebo									
	Common STD 30%			Common STD 40%			Common STD 50%		
	n			n			n		
	nintedanib	placebo	total	nintedanib	placebo	total	nintedanib	placebo	total
20%	37	73	110	64	128	192	100	199	299
30%	17	33	50	29	58	87	45	89	134

If the true standard deviation of change in CRPM relative to baseline lies between 30 and 50 percent, a total number of patients between 110 and 300 would be needed to detect a

treatment group difference of 20% with a power of 90% with a treatment allocation ratio of 1:2 (Nintedanib:Placebo).

However, the key secondary endpoint requires more patients for two reasons: firstly, only patients initially treated with Placebo are analysed in the first step (reducing the actual sample size for this analysis to 2/3 of the total sample size) and secondly, some loss of information is associated with the planned analysis due to the binary state of the endpoint. To be more precise, with n=350 randomised patients, n=233 patients will be initially treated with Placebo and based on the INPULSIS results [[P14-07514](#)], we expect to observe a total of about 40% of disease progression as defined by FVC decline  $\geq 10\%$  or death over week 52 for that treatment group. Using available data from the observational PROFILE study [[R15-1220](#)], we further expect roughly half of the patients to have rising biomarker values (slope greater than zero) and the remaining patients having stable biomarker values (slope less or equal to zero) resulting in about equally sized groups if the rate of change (slope) in blood CRPM from baseline to week 12 is dichotomized. With the stated sample size, an absolute difference in rates of at least 20% (i.e. 30% vs 50% of patients with disease progression) can be detected with a power of 88%.

For these reasons, a sample size of n=350 patients (117 on nintedanib and 233 on placebo) is planned for this study.

Calculations were performed using nQuery Advisor® 6.1.1 statistical package by Statistical Solutions Ltd.

